1.1. NASH: epidemiology, pathogenic mechanisms, clinical relevance and unmet therapeutic needs

Non-alcoholic fatty liver disease (NAFLD) is the commonest cause of chronic liver disease, affecting up to 30% of the general population and 70–90% of obese and type 2 diabetic patients^{1,2}.

NAFLD encompasses a spectrum of histological severity ranging from simple steatosis (SS) to necroinflammation and fibrosis (nonalcoholic steatohepatitis, NASH), which can be differentiated only by liver biopsy. Even though simple hepatic steatosis is a benign condition, up to 30% of patients with NAFLD have the more severe, progressive inflammatory condition known as NASH.

NASH confers an increased risk of cirrhosis, liver failure and hepatocellular carcinoma, and is projected to be the commonest indication for liver transplantation in forthcoming years.

Furthermore, emerging evidence links NAFLD to chronic kidney disease (CKD), as these two conditions share common pathogenic mechanisms^{3,4,5}: consistently, NASH poses a 2.5-fold risk of CKD than the general population⁶ and is becoming the leading cause of combined liver-kidney transplantation^{7,8}.

Despite this, there are no universally accepted pharmacological therapies for NASH. Therefore the need for novel, safe agents in NASH is of paramount importance to prevent disease progression and the accompanying clinical burden.

1.2 Curcumin: mechanisms of action, rationale for liver, metabolic and kidney disease treatment and challenges for NASH therapeutics

Curcumin is a lipophilic polyphenol that is the primary constituent of turmeric (*Curcuma longa*), the most common popular spice in Indian cuisine and a major ingredient of curry powders. In vitro studies showed curcumin has prominent antioxidant, anti-inflammatory, antiproliferative and antifibrotic properties, and targets multiple molecular pathways involved in the pathogenesis of NASH and of chronic kidney disease (CKD)^{9,10}, most prominently nuclear factor-kappa B (NF- κ B)¹¹, a key pro-inflammatory

transcription factor involved in metabolic and nutritional inflammation¹². Dietary curcumin supplementation ameliorated liver disease in preclinical NASH models^{13, 14, 15, 16, 17, 18, 19}

Preliminary human data indicate curcumin supplementation improves surrogate markers of liver disease and of metabolic risk in NAFLD patients^{20, 21}. The combination of curcumin with phospholipids greatly improves oral bioavailability of curcumin, allowing greater systemic concentrations and delivery to target organs^{22, 23}, and curcumin-phosphatidylcholine phytosome complex administration for up to 18 months was well-tolerated, safe²⁴ and improved clinical end-points and inflammatory parameters in patients with osteoarthritis, uveitis and chronic kidney disease (CKD)^{25, 26, 27}.

2. Research Hypothesis and Aims

On the basis of above-mentioned data, we hypothesized that treatment with phytosomal curcumin would result in significant improvement in liver histology in patients with NASH.

Key secondary hypotheses include tolerability and safety of phytosomal curcumin and the potential to improve NASH-related CKD, systemic inflammation, glucose and lipid metabolism.

To test this hypothesis, we designed a phase II, multicentre, double-blinded, placebo-controlled randomized controlled trial (RCT).

3. Study Design setting and timeline

This is a 72-week, investigator-initiated, multicentre, randomized, double-blinded, placebo-controlled trial of treatment with phytosomal curcumin 1 g daily for adults with biopsy-proven NASH. Screening was undertaken within 14 days of randomisation to assess eligibility and collect baseline data. Patients who satisfied the eligibility criteria were randomly assigned (1:1) to receive oral phytosomal curcumin 1 g daily (experimental) or placebo (control). After which, a 12-week washout period is scheduled.

The trial will be conducted at two University hospitals (HUMANITAS Gradenigo, Turin, Italy, and Città della Salute e della Scienza, Turin, Italy) between May 25th, 2018 and Dec 30th, 2022.

The primary outcome measure will be assessed using an intention-to-treat analysis of the proportion of evaluable patients achieving an improvement in liver histology between liver biopsies at baseline (within 6 months of screening) and after 72 weeks of treatment. Histological improvement will be defined as a

combination of resolution of active steatohepatitis and no worsening in fibrosis (assessed by Kleiner Fibrosis score²⁸; detailed in outcome section).

4. Ethics and regulatory approval

The study was funded by Indena Spa, Milan, was conducted in accordance with the ethical principles of the Declaration of Helsinki, was approved by A.O.U San Luigi Gonzaga hospital Ethics Committee (prot. N. 0008942) on May 25th, 2018 and is registered with ISRCTN clinical trial registry (study ID: ISRCTN27793187). All patients gave written informed consent to participate to the study.

End of study

Study will continue until 84 days (12 weeks) after the last enrolled patient or in any case for 6 months since June 2022, depending on levels of enrollment.

5. Methods

5.1 Eligibility criteria

Eligible adult patients (≥ 18 years old) were identified and recruited at the participating trial site centres starting in August 2018 and ending by June 2022, 52 patients will be recruited. Participating trial centres will include the Liver and Metabolic Units at the Humanitas Gradenigo Hospital (Turin) since August 2018), and the Metabolic Unit of Dept of Medical Sciences at the Città della Salute e della Scienza hospital (Turin) since Sept 2018).

All trial participants will give informed written consent at the beginning of the screening visit prior to undergoing any tests and procedures needed to assess eligibility.

Eligibility for the trial will be determined at screening visit 1 by standard blood tests, clinical history (including written-confirmation of drug history where necessary) and physical examination to identify other illnesses or contraindications for participation.

Patients who satisfied the eligibility criteria trial at both sites will be offered to take part in a metabolic mechanistic substudy. The substudy involves a standard Oral Glucose tolerance Test (OGTT) and a standard Oral Fat Tolerance Test (OFTT) on three admissions (at least 24 hours apart from each other) and an indirect calorimetry test at the two participating centres on visits 2 (pretreatment) and 8 (4 weeks

post-treatment). A detailed summary of the metabolic substudy will be published separately. A patient's decision to partake or withdraw from the metabolic substudy will not affect their participation in the main 72-week trial.

A schematic view of trial schedule and design is presented in **Figure 1**.

5.2 Inclusion criteria

The trial entry criteria will be based on a diagnosis of 'definite' NASH on liver biopsy obtained within 6 months of screening. Throughout the study, all liver biopsies will be read centrally by one single (RP) expertised pathologist from the central trial site (HUMANITAS Gradenigo), blinded to clinical and laboratory data and to treatment allocation: prior to randomisation, the liver histopathologist will review all of the liver biopsies of the potential participants to assess whether a diagnosis of 'definite' NASH is present.

A 'definite' diagnosis of NASH is defined if all of the following are present on biopsy: (1) macrovesicular steatosis (>5%); (2) hepatocyte ballooning (\pm Mallory Hyaline) and (3) lobular inflammation (mixed infiltrate, related to foci of ballooning). Only patients with 'definite' NASH will be classified as eligible. All participants are to be ≥ 18 to <70 years of age and have a BMI ≥ 25 kg/m² at screening. Patients with type 2 diabetes mellitus (T2DM) at screening had to have stable glycaemic control (HbA1c <9%) and be managed by either diet and/or a stable dose of metformin/sulfonylurea/s. Patients without a history of T2D prior to the screening visit will undergo a 75-g standard OGTT and/or have their HbA1c measured at screening to determine their glycaemic status and will be labelled as 'non-diabetic' if one or more of the following was confirmed

- Impaired fasting glucose, defined using the European Criteria between 110 and 126 mg/dL.
- IGT, defined as 2 h plasma glucose levels between 140 and 200 mg/dL on the 75 g OGTT.
- Normal Fasting Plasma Glucose <110 mg/dL and normal 2 h plasma glucose levels <140 on the 75 g OGTT.
- HbA1c <6.5%

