5.5 Randomization, stratification and blinding

Randomization and stratification

Participants meeting all the eligibility criteria and providing written informed consent will be randomized centrally on a 1:1 basis to either of the two-study treatments (phytosomal curcumin vs placebo) using computer generated randomization. To ensure even distribution between groups in key baseline covariates, randomization will be stratified into blocks of 4 according to the following variables: diabetes status (present vs. absent), obesity status (present vs. absent), fibrosis stage (stage F3-4 vs. stage 0-2), CKD (present vs. absent). Trial participants will be allocated a unique trial identification number to preserve patient confidentiality and enable the study to be double-blinded. Patients, investigators, assessors, trial site staff, and the sponsor (except for specific laboratory staff and individuals responsible for safety) remained blinded to treatment assignment throughout the trial.

Medication preparation and blinding/unblinding procedures

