9.2 Methods for analysis of primary and secondary outcomes

All evaluable patients will be analysed on an intention-to-treat basis. Evaluable patients are defined as those who have had an end-of-treatment biopsy, irrespective of the amount of treatment they have received.

Patients will be categorised as either achieving the primary histological endpoint (ie, NASH resolution) or not. The proportion of patients with a reported improvement in liver histology will be presented and compared across treatments descriptively with 95% CIs.

The primary analysis will be based on a Cochran–Mantel–Haenszel test based on all randomised patients for the in-trial period with missing data handled as non-responders. The common risk ratio between phytosomal curcumin and placebo was estimated along with exact 95% CI. To test for superiority, the exact two-sided p-value was calculated as the sum of probabilities of outcomes having equal or lower probability than the observed outcome under the null hypothesis.

Adjustments for multiplicity testing in the primary analysis will be performed with the use of the Benjamini-Hochberg procedure; each active-treatment group was compared with the placebo group. Two-sided P values <0.05 were considered statistically significant.

An unpowered, preplanned secondary analysis of categorical outcome measures will be done using the χ^2 test or Fisher exact test, as appropriate, of the difference between the proportions of patients with histological improvement in each treatment group.

A preplanned logistic regression analysis will be undertaken to determine the treatment effect when adjusted for the stratification variables (diabetes status, obesity status, fibrosis stage, CKD status) and trial site. We will calculate adjusted relative risks using the Mantel-Haenszel test. Two-sided P values <0.05 will be considered statistically significant in all analyses.

Continuous secondary outcome measures will be compared between treatment groups using linear

regression, adjusting for parameter baseline values and allocated treatment (as model covariates, equivalent to ANCOVA), with multilevel modelling for key continuous outcome measures to account for repeated measures within each patient.

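### One reassuring screening result is enough for the non-diabetic label, even when another result reaches the protocol's own limit, and the label presumably defines diabetes status throughout the analysis

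*Protocol*

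**What the plan says.** Section 5.2 of the protocol sets the rule for patients with no history of type 2 diabetes before screening. They "will undergo a 75-g standard OGTT and/or have their HbA1c measured at screening", and each "will be labelled as 'non-diabetic' if one or more of the following was confirmed". The four findings are:

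1. "Impaired fasting glucose, defined using the European Criteria between 110 and 126 mg/dL";
2. "IGT, defined as 2 h plasma glucose levels between 140 and 200 mg/dL on the 75 g OGTT";
3. fasting glucose below 110 mg/dL together with 2-hour glucose below 140 mg/dL;
4. HbA1c below 6.5%.

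The section does not say what happens when one result meets an item and another is above the corresponding limit.

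Diabetes status then appears in several places:
- Section 5.5 stratifies randomisation by "diabetes status (present vs. absent), obesity status (present vs. absent), fibrosis stage" and CKD.
- Section 9.2 plans a logistic regression "adjusted for the stratification variables (diabetes status, obesity status, fibrosis stage, CKD status) and trial site".
- The eGFR slope model in section 9.2, also described in section 7, includes diabetes as a covariate.
- Section 9.5 matches placebo donors on diabetes status in the reference-based imputation, and uses it as a subgroup factor for efficacy and safety.

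**The concern.** A rule meant to identify patients without diabetes should not be satisfied by a patient who has a result in the range that the same rule treats as diabetic. Here a single item is sufficient, and each item is silent on at least one of the other measurements. Fasting glucose of 118 mg/dL meets item 1 whatever the HbA1c is; HbA1c of 6.2% meets item 4 whatever the 2-hour glucose is.

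There is a second weakness. Because the testing is OGTT and/or HbA1c, two patients with identical glycaemia can receive different labels according to which test was ordered.

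What is at stake is the accuracy of a baseline variable that is used in five ways. Misclassification weakens stratification and covariate adjustment, mixes patients between the diabetes subgroups, and puts unlike patients in the same donor pool for imputation. The definition cannot wait for an analysis plan, because a stratification factor has to be fixed before the first patient is randomised.

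**Working it through.** The protocol states no figure to reproduce, so the check is of logic. It has three steps.

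**Step 1: enumerate the rule.** The inputs are the cut-offs in section 5.2. Fasting glucose (mg/dL) has three bands: below 110, 110–126, and 126 or above. Two-hour glucose (mg/dL) has three: below 140, 140–200, and 200 or above. HbA1c has two: below 6.5%, and 6.5% or above. That gives 3 × 3 × 2 = 18 combinations when all three results are available. The protocol does not say where a value exactly on an upper limit falls; I count it as above. In the table, 'yes' means labelled non-diabetic as written, with the items met in brackets. An asterisk marks a labelled combination that contains a result at or above a limit.

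| Fasting | 2-hour | HbA1c <6.5% | HbA1c ≥6.5% |
|---|---|---|---|
| <110 | <140 | yes (3, 4) | yes (3)* |
| <110 | 140–200 | yes (2, 4) | yes (2)* |
| <110 | ≥200 | yes (4)* | no |
| 110–126 | <140 | yes (1, 4) | yes (1)* |
| 110–126 | 140–200 | yes (1, 2, 4) | yes (1, 2)* |
| 110–126 | ≥200 | yes (1, 4)* | yes (1)* |
| ≥126 | <140 | yes (4)* | no |
| ≥126 | 140–200 | yes (2, 4)* | yes (2)* |
| ≥126 | ≥200 | yes (4)* | no |

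- Combinations with every result below its limit: 2 × 2 × 1 = 4, all labelled non-diabetic, as they should be.
- Combinations with at least one result at or above a limit: 18 − 4 = 14.
- Of those 14, labelled non-diabetic: 11. Not labelled: 3.
- Labelled in total: 4 + 11 = 15 of 18. If every result had to be below its limit, the total would be 4 of 18.

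Some of the 11 are not marginal. Fasting glucose 110–126 with 2-hour glucose ≥200 and HbA1c ≥6.5% has two of three results above the limits and still meets item 1. Fasting glucose ≥126 with 2-hour glucose ≥200 is labelled non-diabetic if HbA1c is below 6.5%.

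**Step 2: dependence on the test chosen.** Take a patient with fasting glucose below 110, 2-hour glucose 240 mg/dL and HbA1c 6.2%.

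| Tests done | Label as written | If every result obtained must be below its limit |
|---|---|---|
| OGTT only | not labelled non-diabetic | diabetic |
| HbA1c only | non-diabetic | non-diabetic |
| Both | non-diabetic | diabetic |

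Repairing the combination rule alone therefore leaves the last column dependent on the tests done. The tests have to be named as well.

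**Step 3: is the rule corrected elsewhere?** Section 5.5 uses diabetes present versus absent without a definition or a cross-reference. Sections 7, 9.2 and 9.5 do the same. Section 5.2 is the only place that says how status is assigned without a previous diagnosis.

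**The case against.** The bullets can be read as a list of the glycaemic categories that count as non-diabetic: impaired fasting glucose, impaired glucose tolerance, and normal. On that reading 'one or more' is needed, because a patient can have both impairments, and what is missing is a rule for discordant results. This is a fair account of the probable intention, and it rules out one tempting repair: requiring all four bullets. Items 1 and 3 exclude each other, as do items 2 and 3, so nobody could then be non-diabetic. But the text as written does settle discordant cases, and in the wrong direction, since one confirmed item is sufficient.

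The link from section 5.2 to the later uses of diabetes status is an inference. That stands. It is a strong inference, because no other definition exists.

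The consequences are limited, and this also stands. The label is set before randomisation and in the same way for both arms. Section 9.2 names no strata for the primary Cochran–Mantel–Haenszel test, so the label cannot be said to enter it. Four binary factors make 2⁴ = 16 strata for 52 patients, or 52 / 16 = 3.25 per stratum against blocks of 4. Balance within strata is weak anyway, and moving a few patients would change little.

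A reader might also infer that mislabelled patients escape the entry criteria written for type 2 diabetes. The protocol does not support this to any useful extent. The opening text of section 5.3 excludes HbA1c above 9.0% without restricting it to diabetes, and covers TZD and GLP-1 use at screening generally. Section 5.4.3 bars TZDs, GLP-1 agonists and SGLT2 inhibitors for everyone during the trial. A patient labelled through item 4 is already under every HbA1c limit.

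**Conclusion.** The point holds as a defect in a classification rule. As written, a patient without known diabetes who has one reassuring result is labelled non-diabetic despite another result at or above the protocol's own limit. This happens in 11 of the 14 combinations that contain such a result, and the label can also turn on which test was done.

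Two stronger readings are not supported. A reader might infer bias in the treatment comparison or an inflated type I error; a baseline label fixed before allocation produces neither by itself. A reader might also take 11 of 14 as a proportion of patients; it counts logical combinations. The protocol gives neither the share of patients without known diabetes nor any rate of discordant results, so the number affected cannot be estimated.

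What remains is loss of accuracy in the stratification, the logistic and eGFR adjustments, the imputation matching and the diabetes subgroups. This assumes that the section 5.2 label is the diabetes status used in those places. It is worth correcting because the correction is cheap, not because the primary comparison is at risk.

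**What to change.** In section 5.2, replace the one-or-more rule, for stratification and analysis only, with wording such as: a patient without known type 2 diabetes is classified as non-diabetic only if every screening result obtained is below the limit (fasting glucose 126 mg/dL, 2-hour glucose 200 mg/dL, HbA1c 6.5%), and as diabetic otherwise.

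In the same place, remove the and/or choice and name the screening test or tests that determine status in all such patients. Then refer to this single definition in section 5.5 (stratification), section 9.2 (logistic and eGFR models) and section 9.5 (imputation and subgroups).

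If randomisation is complete, keep the strata as randomised. Derive the corrected status from the recorded screening values, blind to allocation, and use it for the covariate, imputation and subgroup analyses. Report how many patients change category and how many lack a named test.

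The cost is a few sentences. The combination rule needs no new test, because it uses results already obtained. Naming the tests adds none if the choice falls on HbA1c and fasting glucose, which are already in the fasting panel in section 8. If 2-hour glucose is included, it adds an OGTT for patients who would otherwise have had HbA1c alone.

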5.3 Exclusion criteria

A detailed summary of the exclusion criteria is provided in **box 1**. In brief, patients with a history or current significant alcohol consumption, poor glycaemic control (HbA1c >9.0%), Child's Pugh B or C cirrhosis or other liver disease aetiology were excluded. The latter was confirmed with a full liver aetiology screen (drug induced, viral hepatitis B/C, autoimmune and genetic) at the screening visit. Past and current alcohol consumption was ascertained by a detailed review of the patient's medical, social history and by a validated, self-administered food frequency questionnaire with reference pictures to remind participants of drink equivalents (see dietary record section). Concomitant use of drugs reported to be inducers (methotrexate, amiodarone, steroids) or potential therapies for NASH (TZDs, GLP-1 analogues, vitamin E), or other known hepatotoxins were assessed during the screening visit (**box 1**).

Box 1. Exclusion criteria

1. Refusal or lacks capacity to give informed consent to participate in the trial.
2. Participation in any clinical trial of an investigational therapy or agent within 12 months of randomisation.
3. Patient (or carer) deemed not competent at using the correct site and technique for subcutaneous injection of the trial treatment (containing dummy drug on practice).
4. NAFLD Activity Score (NAS) <3 on liver biopsy.
5. Child's B or C cirrhosis or clinical evidence of decompensated chronic liver disease: radiological or clinical evidence of ascites, current or previous hepatic encephalopathy and evidence of portal hypertensive haemorrhage or varices on endoscopy.
6. Medical history of multiple drug allergies (defined as anaphylactoid drug reactions in >2 drug groups) or allergy to curry or curcumin-based nutraceuticals
7. Presence of any acute/chronic infections or illness that at the discretion of the chief investigator might compromise the patient's health and safety in the trial.
8. Pregnancy or breastfeeding.
9. Women, of childbearing age, who are not willing to practise effective contraception (ie, barrier, oral contraceptives, impenon or past medical history of hysterectomy) for the 48-week duration of the trial and for 1 month after the last administration of the drug.
10. Liver disease of other aetiologies (ie, drug-induced, viral hepatitis, autoimmune hepatitis, PBC, PSC, haemochromatosis, A1AT deficiency, Wilsons disease).
11. Average alcohol consumption >20 g/d(males) and >10 g/d(females) (as assessed by a validated questionnaire within the last 5 years).
12. Medical/surgery history of; gastric bypass surgery, orthotopic liver transplant (OLT) or listed for OLT, hepatocellular, pancreatic, thyroid carcinoma, acute or chronic pancreatitis and total parenteral nutrition within 6 months of randomisation.
13. Diagnosis of malignancy within the last 3 years (with the exception of treated skin malignancies).
14. Hepatocellular carcinoma: dysplastic or intermediate nodules to be excluded. Regenerative and other nodules to be included at the discretion of the chief investigator.
15. Alanine aminotransferase or aspartate aminotransferase >10×upper limit of normal.

16. >5% weight loss since the diagnostic liver biopsy was obtained.
17. Recent (within 3 months of the diagnostic liver biopsy or screening visit) or significant change (as judged by the chief investigator) in dose of the following drugs: inducers of hepatic steatosis (steroids (oral/intravenous), methotrexate, amiodarone), orlistat and/or multivitamins/vitamin E (containing >200% recommended daily amount; >30 mg/day).
18. Known positivity for antibody to HIV.
19. Currently being treated with renal replacement therapy (ie, haemodialysis or peritoneal dialysis).

Specific exclusion criteria for participants with T2D

1. Participants receiving thiazolidinediones (TZDs), GLP-1-based therapies, SGLT2 inhibitors
3. HbA1c $\geq 10\%$.

Patients who met any of the criteria (listed above) at the screening visit were excluded from trial participation.

